11.7.2 Adverse Events

AEs will be coded using Medical Dictionary for Regulatory Activities (MedDRA, Version 21.0). Non-serious AEs will be reported from the day of first dose of study treatment until at least 28 days after last administration of study drug treatment. Serious adverse events (SAEs) are reported from the time that the patient provides informed consent (i.e., prior to undergoing any study-specific procedure or assessment) until at least 28 days after last administration of study treatment. All SAEs ongoing or occur on Day 28 after the last dose should be followed until resolution or stabilization to a chronic condition, or administration of alternative cancer treatment, whichever is earlier.

Treatment-Emergent AEs (TEAEs)

Treatment emergent AEs (TEAEs) are AEs that begin after first dose of study treatment until 28 days after the last dose of study treatment and prior to the initiation of subsequent anti-cancer therapy.

Baseline signs and symptoms that change attribution or severity during the on-study period are TEAEs. Any ongoing TEAEs that changes in attribution or severity is captured as a new AE. All SAEs ongoing or occur on Day 28 after the last dose should be followed until resolution or stabilization to a chronic condition, or administration of alternative cancer treatment, whichever is later. All AEs will be coded according to the MedDRA Version 21.0 dictionary by system organ class (SOC), preferred term (PT), and severity grade using NCI CTCAE Version 5.0 .

Immune-related Adverse Event (irAE)

An irAE is defined as an AE that is associated with drug exposure and is consistent with an immune-mediated mechanism of action and where there is no clear alternate etiology. irAEs will be identified on the adverse events CRF page.

All adverse event summary tables will be based on the safety population. An overall summary of TEAEs by cohort will be presented.

A breakdown of the number and percentage of patients reporting each adverse event categorized by SOC and PT will be presented. Note that counting will be by patient not event and patients are only counted once within each SOC or PT at the highest grade. The following summaries will be presented:

- Treatment-emergent adverse events
- Treatment-related treatment-emergent adverse events
- Treatment-emergent adverse events leading to all study drug discontinuation
- Treatment-emergent serious adverse events
- Treatment-emergent adverse events resulting in death
- Treatment-emergent adverse events with maximum CTCAE severity grade ≥ 3

All summaries will also be presented by:

- Sitravatinib-related treatment-emergent adverse events
- Nivolumab-related treatment-emergent adverse events
- Sitravatinib- or Nivolumab-related treatment-emergent adverse events
- Pembrolizumab-related treatment-emergent adverse events
- Enfortumab-related treatment-emergent adverse events

- Sitravatinib- or Pembrolizumab- or Enfortumab-related treatment-emergent adverse events

TEAEs will be presented by PT in descending order of frequency. In addition, TEAEs in the Safety population will be presented by grouped grade (Grade 1/2, Grade 3/4, Grade 5 and any) and PT in descending order of frequency.

Immune-related AEs will be summarized separately by SOC, PT, and cohort.

All AEs (including non-treatment-emergent events and serious events) recorded on the CRF will be listed using the all Enrolled Population. A listing of treatment-emergent adverse events leading to dose reduction, interruption or discontinuation of either study drug will be presented separately.

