7.2 Safety Assessments

7.2.1 Medical History

Signs and symptoms of the patient's cancer diagnosis and/or comorbidities present at baseline will be recorded in the CRF as AEs beginning on Day 1 of study treatment and onward throughout the study. The actual date of onset should be recorded in all cases.

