8.2 Adverse Events

An adverse event (AE) is any reaction, side effect or other undesirable medical event that occurs during participation in a clinical trial, regardless of treatment group or suspected causal relationship to study treatment. Assessment of adverse events will include type, incidence, severity (graded by the National Cancer Institute [NCI] Common Terminology Criteria for Adverse Events [CTCAE, Version 5.0]), timing, seriousness, and relatedness to study treatment. A treatment emergent AE (TEAE) is an AE that occurs after the first dose of any study treatment or any preexisting condition that increases in severity after the first dose of study treatment.

All observed or volunteered AEs will be recorded in source documents and reported in the CRF. The best available medical terminology should be used to describe AEs in source documents and CRFs. Terms describing the diagnosis are preferred over individual signs and symptoms of the diagnosis. If determination of the diagnosis is delayed, record signs and symptoms and add the diagnosis as an additional AE when available; follow all recorded AEs to resolution. The actual date of onset should be recorded in all cases. Ongoing AEs that change in attribution or severity should have the date of change entered as the “end date” and a new AE record should be opened with the changed details. Examples of AEs include but are not limited to:

- Signs or symptoms of co-morbidity, illness, or toxicity of study treatment;
- Signs or symptoms of worsening malignancy under study (disease progression assessed by measurement of malignant lesions should not be reported as an AE);
- Laboratory abnormalities (see Section 8.2.1 for guidance for reporting in CRF);
- Hypersensitivity;
- Drug abuse, dependency, overdose, withdrawal or misuse;
- Signs or symptoms of drug interactions;

- Extravasation;
- Exposure during pregnancy or via breastfeeding;
- Medication error; or
- Occupational exposure.

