9.1 Imputation of AEs or Concomitant Medications

Start Date

If the start date of AE is completely missing (i.e., the day, month, and year are all unknown), the start date will be set to the date of first dose of study medication. No imputation will be performed for medications with completely missing start dates.

Missing Day Only

- If the month and year of the incomplete date are the same as the month and year of the **first dose date**, then the day of the **first dose date** will be assigned to the missing day.
- If either the year is before the year of the **first dose date** or if years are the same but the month is before the month of the **first dose date**, then the last day of the month will be assigned to the missing day.
- If either the year is after the year of the **first dose date** or if both years are the same but the month is after the month of the **first dose date**, then the first day of the month will be assigned to the missing day.

Missing Month Only

- The day will be treated as also missing and both month and day will be replaced according to the below procedure.

Missing Day and Month

- If the year of the incomplete date is the same as the year of the **first dose date**, then the day and month of the **first dose date** will be assigned to the missing fields.

- If the year of the incomplete date is not the same as the year of the **first dose date**, then January 1 will be assigned to the missing fields.
- If the stop date is complete and the imputed start date is after the stop date, then the start date will be imputed using the stop date.

Stop Date

Missing Day Only

- If the month and year of the incomplete date are the same as the month and year of the **last visit date**, then the day of the **last visit date** will be assigned to the missing day.
- If either the year is before the year of the **last visit date** or if both years are the same but the month is before the month of the **last visit date**, then the last day of the month will be assigned to the missing day.
- If either the year is after the year of the **last visit date** or if both years are the same but the month is after the month of the **last visit date**, then the first day of the month will be assigned to the missing day.

Missing Month Only

- The day will be treated as missing and both month and day will be replaced according to the below procedure.

Missing Day and Month

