11.5 Medical History

Medical history will be tabulated by system organ class (SOC) and preferred term (PT) using counts and percentages for the Safety population. Medical history will be coded according to Medical Dictionary for Regulatory Activities (MedDRA, Version 21.0). Medical history will be listed by patient.

Baseline Signs and Symptoms

Signs and symptoms of the patient's cancer diagnosis and/or comorbidities present prior to Day 1 of study treatment dosing are recorded in the CRF as primary disease history.

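### The SAP counts a baseline symptom whose grade changes in either direction as a treatment-emergent adverse event; the protocol counts only one that worsens

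*SAP*

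**What the plan says.** Protocol 8.2 defines a TEAE in two limbs. The first is an adverse event occurring after the first dose of any study treatment. The second covers conditions already present, and there the test is "any preexisting condition that increases in severity after the first dose of study treatment".

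SAP 11.7.2 starts with a time window: "Treatment emergent AEs (TEAEs) are AEs that begin after first dose of study treatment until 28 days after the last dose of study treatment", and before any subsequent anti-cancer therapy. It then adds a rule for conditions already present: "Baseline signs and symptoms that change attribution or severity during the on-study period are TEAEs". A third sentence deals with events that are already TEAEs: "Any ongoing TEAEs that changes in attribution or severity is captured as a new AE".

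Two recording rules bear on this. Under Protocol 8.2, "Ongoing AEs that change in attribution or severity should have the date of change entered as the" end date, and a new record is opened with the changed details. Under Protocol 7.2.1, signs and symptoms of the cancer or of comorbidities "present at baseline will be recorded in the CRF as AEs beginning on Day 1 of study treatment". SAP 11.5 puts the same information elsewhere: signs and symptoms "present prior to Day 1 of study treatment dosing are recorded in the CRF as primary disease history".

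**The concern.** Severity grades have a direction, and the SAP sentence ignores it. A symptom that was worse before treatment and better on treatment satisfies the rule just as one that worsened does. Safety is a secondary endpoint and no cohort has a control arm, so nothing offsets records that enter the TEAE tables for this reason. The error also runs one way: counting improvements can add patients to a table or raise the grade shown, but it cannot remove anyone.

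The eligibility rules allow such cases. Inclusion criterion 4 admits patients to Cohorts 1 to 8 with any-grade alopecia and with dysgeusia or peripheral neuropathy up to Grade 2; the neuropathy limit is stricter in Cohorts 9 and 10. Cohorts 7 and 8 enroll after an antibody-drug conjugate. If residual Grade 2 neuropathy in such a patient is recorded as a baseline symptom and eases to Grade 1, the SAP rule tabulates it as neuropathy emerging on sitravatinib plus nivolumab.

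**Working it through.** There is no figure in the plan to reproduce. The check applies each definition to the possible changes in a symptom present at baseline. The inputs are the pre-existing-condition limb of Protocol 8.2 and the baseline-symptom sentence of SAP 11.7.2.

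| Change after first dose | Protocol 8.2, pre-existing limb | SAP 11.7.2 |
|---|---|---|
| Grade 2 to Grade 3 | TEAE | TEAE |
| Grade 2, unchanged | not a TEAE | not a TEAE |
| Grade 2 to Grade 1 | not a TEAE | TEAE, Grade 1 |
| Grade 4 to Grade 3 | not a TEAE | TEAE, Grade 3 |
| Same grade, attribution changed | not a TEAE | TEAE |

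The documents agree in the first two cases and disagree in the last three. If the SAP sentence required an increase in severity and dropped the attribution trigger, they would agree in all five.

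**Does any other SAP text restrict the rule to worsening?** I found none. The time window does not: a record opened when the grade falls starts after first dose and so fits the window as well. The SAP describes no step that compares a record with the baseline grade.

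**Which tables are reached?** SAP 11.7.2 plans all-cause TEAE summaries by system organ class and preferred term, by grouped grade, and for maximum Grade 3 or higher. None filters on relatedness. The Grade 2 to Grade 1 case enters the first two and the Grade 4 to Grade 3 case enters all three. The treatment-related and drug-specific summaries are reached only if the investigator attributes the record to a study drug.

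**What does the counting rule do?** A patient is counted once per term, at the highest grade. An improvement record therefore adds a patient to a term only if that patient has no other TEAE of that term. It raises the grade shown only if its grade exceeds those of the patient's other TEAEs of that term. The rule does not remove a patient whose sole event for a term is an improvement. Full resolution ends the event, so the problem is confined to partial improvement and to attribution changes.

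**Do the records exist?** Under Protocol 7.2.1 together with 8.2, yes: the baseline symptom is on the adverse event pages and is closed and reopened when its grade changes. Under SAP 11.5 the symptom sits in disease history, and there may be no adverse event record to reopen. The documents do not settle which describes the CRF, so the number of affected records depends on that unresolved conflict.

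**The case against.** Five points can be made for the plan.

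- **The SAP may differ from the protocol.** Protocol 9 allows the SAP to modify its plans, and the SAP change history shows that version 3.0 revised the TEAE definition to match another study. Departure alone is therefore not an error. But the change history gives no reason for treating improvement as emergence.
- **The counting rule limits the damage.** This stands as a limit. In this study's own interim data (Protocol 1.3.3.2), treatment-related fatigue was reported in 58% and decreased appetite in 38% of 40 patients. For common terms like these, many patients would be counted anyway.
- **Toxicity is read from the related tables.** Attribution to each drug is collected, and the SAP plans drug-related summaries. This narrows the effect to the all-cause tables but does not remove it there.
- **The CRF may hold baseline symptoms in disease history.** If so, the record-splitting route may not operate. The SAP sentence would still classify the symptom as a TEAE.
- **An improved record might pass the protocol's first limb** as an event occurring after first dose. That reading would leave the explicit requirement of an increase with no work to do.

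A reader might also infer that the missing-date rule in SAP 9.1 makes matters worse, since for an adverse event with a wholly unknown onset "the start date will be set to the date of first dose of study medication". That is a separate question. It has nothing to do with direction of change, the protocol asks for the actual onset date in every case, and an onset set to the first-dose date counts only if the window is read to include that day. No change to SAP 9.1 is proposed here.

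**Conclusion.** The SAP rule is wrong as written. It adds partly improved baseline symptoms, and symptoms whose attribution alone changes, to the all-cause TEAE tables, which the protocol's pre-existing-condition limb would not do. The rule should be corrected before the safety tables are produced. It does not touch the response endpoint.

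The conclusion about the definition rests only on the wording of the two sections. The number of affected records rests on which recording rule the CRF follows, and the effect on TEAE incidence cannot be computed.

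A reader might infer a size by multiplying a guessed prevalence of baseline symptoms by a guessed rate of improvement. Neither input is in the documents, and the product would ignore the once-per-term rule. The adverse event lists in Protocol 1.3.3.2 are no yardstick for it either: they report treatment-related events, with a cut at 20% for events of any grade, while this point concerns all-cause TEAEs. The rates reported there and for enfortumab in Protocol 1.6.3.4 describe events on treatment, not symptoms still present at entry. A reader might also suppose that the added events would fall mainly in responders. Nothing in the documents shows that.

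**What to change.** In SAP 11.7.2, replace the baseline-symptom sentence with: *Baseline signs and symptoms that increase in severity above the baseline grade after the first dose of study treatment are TEAEs.* Add that a record opened only because a grade fell continues the original event and is not a new TEAE.

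Either remove the attribution trigger or keep it as a stated and justified departure from Protocol 8.2. Removing it is what brings the two definitions into agreement.

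Reconcile Protocol 7.2.1 with SAP 11.5 on where baseline symptoms are recorded, checking against the CRF version on which the SAP was built.

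The cost is SAP wording and a derivation that compares each record with the baseline grade. Neither document describes a link between a closed record and the one that replaces it, so records may have to be matched by patient, term and dates. No new data are needed. SAP 5.0 provides for an amended version before database lock. If lock has passed, SAP 4.0 already requires departures from the SAP to be described in the clinical study report.

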5.1.3 Sitravatinib Dose Modification and Discontinuation

This protocol provides guidance for dose modification of sitravatinib (i.e., interruption, dose reduction or discontinuation) for AEs attributed to sitravatinib. For adverse events attributed to nivolumab, pembrolizumab or enfortumab see the current [OPDIVO US Prescribing Information](#), [KEYTRUDA US Prescribing Information](#) and [PADCEV US Prescribing Information](#), Section 5.2.4 for dose nivolumab modifications, Section 5.3.4 for dose for pembrolizumab modifications, and Section 5.4.4 for dose for enfortumab modifications.

Available dose levels for each of the sitravatinib formulations are outlined in [Table 5](#) and [Table 6](#). Dose modifications guidelines for the malate capsule formulation ([Table 6](#))

follow comparable dose reduction proportions used for the free base capsule formulation. Guidelines for sitravatinib dose modifications to be implemented to manage adverse events are described in Section 5.3.1 and 5.3.3. Once the dose has been reduced, re-escalation is generally not recommended but may be considered on a case-by-case basis with approval from the Medical Monitor. If the administration of sitravatinib is interrupted for reasons other than toxicity, then treatment with the study drug may be resumed at the same dose.

The starting dose for sitravatinib using the free base capsule formulation is 120 mg QD.

Table 5: Sitravatinib Sequential Dose Reductions for Individual Patients on Free Base Capsule Formulation

120 mg once daily
80 mg once daily
60 mg once daily
40 mg once daily

The starting dose for sitravatinib using the malate capsule formulation is 100 mg QD.

Table 6: Sitravatinib Sequential Dose Reductions for Individual Patients on Malate Capsule Formulation

100 mg once daily
70 mg once daily
50 mg once daily
35 mg once daily
20 mg once daily*

* This dose level is only available for Cohorts 9 and 10.

In the event of sitravatinib-related AE, dose reduction with continuous treatment is preferred over repeated dose interruption. If treatment with sitravatinib is delayed for ≥ 14 days, then resumption at a reduced dose should be considered. If treatment with sitravatinib is withheld for ≥ 28 consecutive days, then permanent discontinuation of sitravatinib should be considered. If one study drug is interrupted or discontinued, administration of the other study drug may continue at the discretion of the Investigator.

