5.5.5 Management of Immune-Related Adverse Events

Sitravatinib has not been associated with immune-mediated AEs. However, the potential exists for one or more of the treatments to contribute to immune-mediated AEs associated with nivolumab or pembrolizumab treatment. In the event of a Grade 2 immune-related AE during study treatment, administration of study treatments (sitravatinib and nivolumab, or sitravatinib, pembrolizumab and enfortumab) should be interrupted until the event stabilizes to Grade ≤ 1 (consistent with guidance provided in the [OPDIVO US Prescribing Information](#) and [KEYTRUDA US Prescribing Information](#)). At the time of resumption of sitravatinib dosing, a dose reduction may be implemented at the discretion of the Investigator.

Management of Grade 3 and 4 immune-mediated adverse events should be performed in accordance with the [OPDIVO US Prescribing Information](#) and [KEYTRUDA US Prescribing Information](#). However, recurrent Grade 3, or any Grade 4, immune-mediated adverse events should generally be managed with permanent discontinuation of nivolumab or pembrolizumab. Administration of sitravatinib should be interrupted and may be resumed at the same or lower dose at the discretion of the Investigator after the event stabilizes to Grade ≤ 1 .

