11.1 Patient Disposition

The number and percentage of patients enrolled and treated in the study will be presented. The number and percentage of patients and each population to which they belong will be presented as well as the number and percentage of patients who withdrew from the study and a breakdown of the corresponding reasons for withdrawal and the number and percentage of patients who discontinued nivolumab, sitravatinib, pembrolizumab, or enfortumab with the corresponding reasons. Summaries will be reported by cohort. The number of patients enrolled by site and across sites will be presented. Disposition will be summarized descriptively by cohort and for all cohorts combined.

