Descriptive statistics will be provided separately for each study drug, for the duration of exposure (weeks), the total number of cycles started, number of days on sitravatinib, cumulative dose received (mg) and absolute and relative dose intensities as well as compliance.

Number and percentage of patients with at least 1 dose reduced and reason for dose reduction (only for sitravatinib), at least 1 dose interrupted and reasons for dose interruption will be presented separately for each study drug.

Information regarding patients' dosing regimens will be listed separately for each study drug.

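### The only table of adverse events leading to discontinuation counts stops of all study drugs; none shows which events ended sitravatinib, or any other drug, alone

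*SAP*

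**What the plan says.** **Planned adverse-event output.** SAP 11.7.2 names a set of summaries by system organ class and preferred term. The one concerned with stopping treatment is "Treatment-emergent adverse events leading to all study drug discontinuation". The section then says "All summaries will also be presented by" and gives six groupings by the drug to which the event was attributed. Single-drug action appears at event level in one place: "A listing of treatment-emergent adverse events leading to dose reduction, interruption or discontinuation of either study drug will be presented separately".

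**Other planned output.** SAP 11.1 tabulates "the number and percentage of patients who discontinued nivolumab, sitravatinib, pembrolizumab, or enfortumab with the corresponding reasons", and adds that "Disposition will be summarized descriptively by cohort and for all cohorts combined". SAP 11.7.1 tabulates interruptions for each drug, and dose reductions for sitravatinib, with reasons. It does not tabulate discontinuation.

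**Treatment rules.** Protocol 5.1.3 states: "If one study drug is interrupted or discontinued, administration of the other study drug may continue at the discretion of the Investigator". Sections 5.2.4, 5.3.4 and 5.4.4 carry equivalent wording for the other agents. Section 5.5.1.3.1 and Table 9 end sitravatinib for Grade 4 hypertension. Table 10 ends sitravatinib for Grade 3/4 transaminase rises that have not resolved within 29 days. Under section 5.5.5, Grade 4 immune-mediated events, and Grade 3 ones that recur, "should generally be managed with permanent discontinuation of nivolumab or pembrolizumab", while sitravatinib is interrupted and may be resumed.

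**The concern.** A combination regimen can fail on tolerability one drug at a time. A discontinuation table that requires all drugs to be stopped does not record those failures. The rules above suggest that the characteristic toxicities of each agent are the ones most likely to end that agent alone: hypertension and transaminase rises for sitravatinib, immune-mediated events for the checkpoint inhibitor.

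Safety and tolerability of the combination is a secondary objective, and sitravatinib is the investigational drug. A reader of the report will want to know which events, at what grade and with what attribution, made patients give up sitravatinib for good. The protocol reports this kind of result for the partner drugs. In Protocol 1.5.3.5, adverse events ended pembrolizumab in 8% of patients in KEYNOTE-045, most commonly pneumonitis (2%). In Protocol 1.6.3.4, they ended enfortumab in 16% of patients in EV-201, most commonly peripheral neuropathy (6%). As planned, no table would give the same result by event term for sitravatinib.

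**Working it through.** The plan states no figure on this point, so the check is to follow a patient through the planned outputs.

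**Step 1. Which outputs show what.** Take a patient in Cohorts 1 to 8 who has Grade 4 hypertension judged related to sitravatinib, stops sitravatinib permanently, and stays on nivolumab until progression.

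| Planned output | Does the patient or event appear? | Is the event shown to have ended sitravatinib? |
|---|---|---|
| All-drug discontinuation table (SAP 11.7.2) | No: nivolumab continued and was not stopped for this event | No |
| Its sitravatinib-related version | No: it is a subset of the table above | No |
| General, related and Grade 3 or higher TEAE tables (11.7.2) | Yes | No: the event is not flagged |
| Disposition (11.1) | Yes: counted under sitravatinib with a reason | Reason only; no term, grade or relatedness is specified |
| Reductions and interruptions (11.7.1) | Permanent stops are not covered | No |
| Listing of TEAEs leading to dose action (11.7.2) | Yes | Yes, but as a line in a listing |

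The same holds with the drugs exchanged. An immune-mediated event that ends nivolumab while sitravatinib resumes is in the TEAE tables and the immune-related table, unflagged. It is counted in disposition, and its link to the stop is visible only in the listing.

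**Step 2. Do the attribution splits repair this?** No. They divide events by suspected cause. Which drug was stopped is a separate variable, so splitting the all-drug table by cause cannot restore an event that never entered it.

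**Step 3. What the table does capture.** Some events stop everything. Protocol 5.5.6, for example, calls for permanent discontinuation of all study treatments in a Hy's Law case. The table is useful for those events and should stay.

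**Step 4. Is the term clear?** No. If one event ends sitravatinib in Cycle 2 and a different event ends nivolumab in Cycle 5, the SAP does not say whether the first event, the second, both or neither qualifies. In the listing, *either* presupposes two drugs, whereas Cohort 9 receives three.

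**Step 5. How far can a listing substitute?** SAP 11.7 presents safety by cohort and for all cohorts combined. The planned ceilings are 40 patients in each of Cohorts 1 to 4, 45 evaluable in each of Cohorts 5 and 6, about 55 evaluable in each of Cohorts 7 and 8, and 30 in the Cohort 9 lead-in. SAP Figure 1 notes that the Cohort 9 expansion and Cohort 10 will not open.

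(4 × 40) + (2 × 45) + (2 × 55) + 30 = 160 + 90 + 110 + 30 = 390

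A listing can be read by eye in one small cohort. Across up to 390 planned patients, with reductions and interruptions in the same listing, the reader would have to build the table by hand.

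**The case against.** The strongest reply is that the SAP already covers single-drug stops. Disposition gives counts and percentages for each of the four drugs with reasons, by cohort and combined. The events themselves are tabulated by system organ class and preferred term as TEAEs, as related TEAEs and as Grade 3 or higher TEAEs; immune-related events have their own summary, and AST and ALT have shift tables. The listing names the events behind each stop. Protocol 9.5.1 promises only separate summaries of significant events, with study discontinuation as its example, so no commitment is broken. These are small single-arm cohorts, and nothing inferential hangs on the table.

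Most of that stands, and it rules out two stronger readings that a reader might infer. The first is that toxicity ending one drug is missing from the tolerability tables. It is not: the patients are in disposition and the events are in the general tables. The second is that the report would understate how often toxicity ends sitravatinib. That does not follow either, because frequency by drug and reason is what SAP 11.1 provides, and a table labelled for all-drug discontinuation does not understate the quantity it names.

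What the reply leaves open is the link between event term, grade and attribution on one side and a single-drug stop on the other. No planned table shows it. The small-cohort argument is also weaker for the combined safety presentation.

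A fair objection concerns volume. With the six attribution groupings plus an overall version applied to six discontinuation definitions (all, any and four single drugs), the outputs would rise from 1 × 7 = 7 to 6 × 7 = 42, many of them inapplicable to a given cohort. The fix should avoid that.

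**Conclusion.** The point holds in a narrow form. The SAP plans one discontinuation table by event term, confined to an undefined all-drug category, for regimens in which the protocol permits, and in places directs, stopping one drug alone. The number of patients stopping each drug is covered. Which events ended sitravatinib, or another single drug, is tabulated nowhere.

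No percentage can be attached. The documents give no rate of adverse events that end one drug only, and assuming one would merely return the assumption as the result.

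The conclusion rests on three things. First, *all study drug discontinuation* is read as every drug stopped. If *any* was meant, the wording still needs correcting and tables for each drug would still be absent. Second, adverse event is taken to be one of the disposition reasons; SAP 11.1 does not list the categories, but Protocol 6.5 includes it among the criteria for stopping study medication. Third, the sitravatinib rules cited name sitravatinib only. The partner drug is then governed by its own labelling and the investigator's discretion, so single-drug stops are provided for, not guaranteed.

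This is an inexpensive improvement to reporting on a secondary objective. It is not a conflict with the protocol, and it affects no endpoint, analysis population or enrolment decision.

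**What to change.** In SAP 11.7.2:

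1. Define the all-drug category, including how it treats different events that end different drugs at different times, and keep that table.
2. Add a table by system organ class and preferred term, with grade, of TEAEs leading to discontinuation of any study drug.
3. Add the same table for each drug given in the cohort: sitravatinib and nivolumab for Cohorts 1 to 8; sitravatinib, pembrolizumab and enfortumab for Cohort 9.
4. For these tables, limit the attribution splits to all events and related events.
5. In the listing, change *either* to *any* study drug so that it fits Cohort 9.

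The additions are five definitions (any drug and four single drugs) in two versions each, so 5 × 2 = 10 outputs built on one table shell. The link between each event and the action taken on each drug is already needed for the planned listing, so no new data collection should be required. The SAP describes itself as a living document to be amended before database lock, which gives a route for the change. No treatment rule is affected.
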